## Statistical Analysis Plan (SAP)

---

**Table 1: Schedule of Assessments for PsA Subjects**

In the original protocol:

## Statistical Analysis Plan (SAP)

[figure not shown]
Visit a	1	2	3	4	5	6	7	8	9	10	11	12	13	14	15	16	17	18	19
	0Y BL					1Y 4W				2Y		~2Y 6M		~3Y		~3Y 6M		~4Y	EoT/ FU
Week (± 7D)	0b	8	20	32	44	56	68	80	92	104	116	128	140	152	164	176	188	200	208c
Written informed consent	X																		
Inclusion/Exclusion criteria	X																		
Demographic information d	X																		
Physical examination	X					X				X				X			X	X	
Vital signs	X	X	X	X	X	X		X		X		X		X		X	X	X	
AEs/Concomitant medications e	X	X	X	X	X	X	X	X	X	X	X	X	X	X	X	X	X	X	
Medical/Medication history e	X																		
ECG	X					X				X				X			X	X	
IMP administration f	X	X	X	X	X	X	X	X	X	X	X	X	X	X	X	X	X	X	
Hematology/chemistry/urinalysis g	X					X				X				X			X	X	
Lipids h	X					X				X				X			X	X	
Urine pregnancy test i	X	X	X	X	X	X	X	X	X	X		X		X		X	X	X	
hsCRP and ESR i	X	X		X		X				X			X			X	X	X	
Anti-drug antibodies	X					X				X			X			X	X	X	
PK sample h	X					X				X			X			X	X	X	

## Statistical Analysis Plan (SAP)

Visit a	1	2	3	4	5	6	7	8	9	10	11	12	13	14	15	16	17	18	19
	0Y BL					1Y 4W				2Y		~2Y 6M		~3Y		~3Y 6M		~4Y	EoT/ FU
Week (± 7D)	0b	8	20	32	44	56	68	80	92	104	116	128	140	152	164	176	188	200	208c
Tender and Swollen Joint counts	X	X	X	X	X	X	X	X	X	X		X		X		X		X	X
PGA of disease activity VAS	X	X	X	X	X	X	X	X	X	X		X		X		X		X	X
PsA pain VAS	X	X	X	X	X	X	X	X	X	X		X		X		X		X	X
PtGA of disease activity VAS	X	X	X	X	X	X	X	X	X	X		X		X		X		X	X
HAQ-DI	X	X	X	X	X	X	X	X	X	X		X		X		X		X	X
SF-36	X					X				X				X			X	X	
C-SSRS j	X	X	X	X	X	X	X	X	X	X		X		X		X		X	X

Abbreviations: AE = adverse event; BL = Baseline; C-SSRS = Columbia-Suicide Severity Rating Scale; D = days; ECG = electrocardiogram; ESR = erythrocyte sedimentation rate; EoT = End of Treatment; FU = Follow-up; HAQ-DI = Health Assessment Questionnaire Disability Index; hsCRP = high sensitivity C-reactive protein; IMP = investigational medicinal product; M = months; PGA = Physician Global Assessment; PK = pharmacokinetic; PsA = psoriatic arthritis; PtGA = Patient Global Assessment; SF-36 = 36-item Short Form; VAS = Visual Analog Scale; W = weeks; Y = year(s).

a Interim visits will occur at 4-week intervals (± 7 days) between the scheduled visits for 12-weekly IMP administration. Collection of AEs and concomitant medications will also be performed, and any other unscheduled safety assessment deemed appropriate in the opinion of the Investigator to ensure subject safety. A decision to remove 1 or more treatment arms from the long-term extension study may occur as information from parent studies becomes available. Subjects already enrolled in the long-term extension study may be switched to selected dose regimens for continued evaluation at that time. This decision is anticipated to occur approximately 1 year after the start of the long-term study. In addition, following completion and database lock of the

[figure not shown]
## Statistical Analysis Plan (SAP)

parent PsA Phase 2 study, the long-term extension study will have the option to become open-label for these subjects, and interim visits for IMP administration will continue only for subjects receiving a 4--weekly dosing regimen.

- b The BL visit of the study Visit 1 (Week 0, Day 1) will be the same as Visit 16, Week 52 of parent PsA study (or later for subjects who entered the wash-out phase from the parent study due to the timing of study site activation of the long-term extension study).
- c Subjects who withdraw from IMP at any time will complete the EoT/FU assessments approximately 4 weeks after administration of the last dose of IMP.
- d To include body weight only. Other demographic data including date of birth, sex, ethnicity, and subject height will be obtained from the parent study.
- e Report all AEs, SAEs, and concomitant medications that occur after signing of the Informed Consent Form for the long-term study. Any occurring prior to signing the Informed Consent Form for the long-term study should be recorded under Medical/Medication history.
- f IMP administration will occur on Day 1 of Week 0.
- g Blood samples are to be collected (pre-dose where applicable), after ECG and vital sign measurements.
- h At visits where lipids are assessed, the blood samples are to be collected (pre-dose where applicable) after 8 hours fasting, following ECG and vital sign measurements.
- i Urine pregnancy tests and ESR will be performed at the study site using materials supplied by the central laboratory.
- j Evaluations will continue from the parent study using the version with questions referring to 'since the last visit'. No lifetime version will be repeated at BL

# Statistical Analysis Plan (SAP)

Visit a	1	2	3	4	5	6	7	8	9	10	11	12	13	14	15	16	17	18	19
	1Y BL					2Y				3Y					4Y			EoT/ FU	
Week (± 7D)	0b	8	20	32	44	56	68	80	92	104	116	128	140	152	164	176	188	200	208c
Written informed consent	X																		
Inclusion/Exclusion criteria	X																		
Demographic information d	X																		
Physical examination	X					X				X				X			X	X	
Vital signs	X	X	X	X	X	X	X	X	X	X	X	X	X	X	X	X	X	X	
AEs/Concomitant medications e	X	X	X	X	X	X	X	X	X	X	X	X	X	X	X	X	X	X	
Medical/Medication history e	X																		
ECG	X					X				X				X				X	
IMP administration f	X	X	X	X	X	X	X	X	X	X	X	X	X	X	X	X	X	X	
Hematology/chemistry/urinalysis g	X		X			X				X				X			X	X	
Lipids h	X		X			X				X				X			X	X	
Urine pregnancy test i	X	X	X	X	X	X	X	X	X	X	X	X	X	X	X	X	X	X	
hsCRP and ESR i	X		X			X				X				X			X	X	
Anti-drug antibodies	X		X			X				X				X			X	X j	
PK sample h	X		X			X				X				X			X	X	
C-SSRS k	X	X	X	X	X	X	X	X	X	X	X	X	X	X	X	X	X	X	

## Statistical Analysis Plan (SAP)

---

Abbreviations: AE = adverse event; BL = Baseline; C-SSRS = Columbia-Suicide Severity Rating Scale; D = days; ECG = electrocardiogram; ESR = erythrocyte sedimentation rate; EoT = End of Treatment; FU = Follow-up; hsCRP = high sensitivity C-reactive protein; IMP = investigational medicinal product; M = months; PK = pharmacokinetic; PsA = psoriatic arthritis; W = weeks; Y = year(s).

- a Visits will be scheduled every 12 weeks in the first two years, followed by every 24 weeks in the last two years. Collection of AEs and concomitant medications, as well as any unscheduled safety assessment deemed appropriate in the opinion of the Investigator to ensure subject safety, will be performed at each visit. In addition, following completion and database lock of the parent PsA Phase 2 study, the long-term extension study will have the option to become open-label for these subjects.
- b The BL visit of the study Visit 1 (Week 0, Day 1) will be the same as Visit 16, Week 52 of parent PsA study (or later for subjects who entered the wash-out phase from the parent study due to the timing of study site activation of the long-term extension study).
- c Subjects who withdraw from IMP at any time will complete the EoT/FU assessments approximately 4 weeks after administration of the last dose of IMP.
- d To include body weight and height only. Other demographic data including date of birth, sex, and ethnicity will be obtained from the parent study.
- e Report all AEs, SAEs, and concomitant medications that occur after signing of the Informed Consent Form for the long-term study. Any occurring prior to signing the Informed Consent Form for the long-term study should be recorded under Medical/Medication history.
- f IMP administration will occur on Day 1 of Week 0; followed by subsequent dosing Q12 weeks.
- g Blood samples are to be collected (pre-dose where applicable), after ECG and vital sign measurements.
- h At visits where lipids are assessed, the blood samples are to be collected (pre-dose where applicable) after 12 hours fasting, following ECG and vital sign measurements.
- i Urine pregnancy tests will be performed by using a urine dip stick. ESR will be performed at the site using materials supplied by the central laboratory. hsCRP samples will be sent to the central lab and analyzed by central lab.
- j A final anti-drug antibodies sample needs to be collected after 20 weeks from last dose.
- k Evaluations will continue from the parent study using the version with questions referring to 'since the last visit'. No lifetime version will be repeated at BL.

# Statistical Analysis Plan (SAP)

## 4 STUDY ENDPOINTS

### 4.1 Efficacy endpoint

The efficacy endpoints are:

- The proportion of subjects who achieve ACR20 at measured time points,
- The proportion of subjects who achieve ACR50 at measured time points,
- The proportion of subjects who achieve ACR70 at measured time points,
- Individual components of ACR response at measured time points:
  - tender joint counts (68),
  - swollen joint counts (66),
  - PGA of disease activity (VAS),
  - PtGA of disease activity (VAS),
  - patient's pain assessment (VAS),
  - patient's self-assessed disability (HAQ-DI),
  - acute-phase hsCRP,
  - ESR.
- SF-36 at measured time points.

The ACR20 is defined as at least a 20% improvement from Baseline in both tender joints (68) and swollen joints (66) along with at least a 20% improvements in 3 of 5 other items: 1) the Physician Global Assessment (PGA) of disease activity (as measured using a VAS), 2) the Patient Global Assessment (PtGA) of disease activity (as measured using a VAS), 3) patient pain assessment (as measured using a VAS), 4) patient self-assessed disability (as measured using the HAQ-DI), and 5) acute-phase CRP.

Similarly, ACR50 is defined as at least a 50% improvement from Baseline in both tender joints (68) and swollen joints (66) along with at least a 50% improvements in 3 of 5 other items listed above; ACR70 is defined as at least a 70% improvement from Baseline in both tender joints (68) and swollen joints (66) along with at least a 70% improvements in 3 of 5 other items listed above.

Baseline used to derive ACR is the baseline value for each component from parent study.

If the value in any of the components at a time point is missing, the component variables that are not missing will be used to determine the response status. As a general principle, if there are sufficient

# Statistical Analysis Plan (SAP)

non-missing components to determine whether the ACR endpoint is a response or non-response, then ACR endpoint is not missing, else if the available non-missing components are not sufficient to determine the response status of ACR endpoint then it is considered missing.

If the baseline value of any component is equal to 0, the following algorithm will be used in evaluating the percent change from baseline:

- If change from baseline is also equal to 0, then percent change from baseline is set to be 0%;
- If change from baseline is  $> 0$ , then percent change from baseline is set to be 9999999%.

These imputed percentages of 0% and 9999999% will be used to derive the ACR endpoints only.

Any ACR endpoint that utilizes these imputed values to achieve response will be flagged in by-subject listings.

In addition, any hsCRP value below the LLOQ will be reported as “<0.xxx” in database and will be set to the LLOQ and used in analyses.

HAQ-DI derivation is described in [Section 12.1.1](#)

SF-36 is derived per [Section 12.1.2](#)

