# Statistical Analysis Plan (SAP)

## 3 STUDY DESIGN

### 3.1 General study design

This is a long-term extension study of tildrakizumab in subjects with PsA who have previously completed the treatment period of studies with tildrakizumab. Eligible PsA subjects who have previously completed the treatment period of Phase 2b study CLR\_16\_23 (hereafter referred to as the parent Phase 2 study) will be entered into this long-term extension study. Other subjects, including those completing the treatment period of Phase 3 PsA tildrakizumab studies, may also be eligible to enter this long-term extension study.

Up to 286 subjects with PsA could be enrolled from the parent Phase 2 study. Additional subjects may be enrolled from other parent studies. No randomization will occur for this long-term extension study. Treatment allocation will be based upon the dose regimen assigned at the end of the treatment period in the parent study, with all subjects receiving tildrakizumab in the long-term extension study. The eligible subjects will continue to be administered one of the following dose regimens – 200 mg Q4W, 200 mg Q12W or 100 mg Q12W to maintain the blind of the ongoing parent study to at least Week 52 of the long-term extension study. Thereafter, all subjects began migrating to receive 100 mg tildrakizumab SC injection Q12 weeks in an open-label fashion.

Note: eligibility for the long-term extension study will be based on response criteria at Week 52 [using Week 48 laboratory data from the parent study where relevant for calculations] regardless of timing of subject entry. Subject eligibility for continuation to the long-term extension study based on the clinical response criterion will be determined by the interactive voice response service (IVRS).

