### 7.2 Handling of missing data and outliers

#### 7.2.1 Missing data analysis methods

In general, missing values for any of efficacy and safety endpoints will not be imputed when summarizing these endpoints using descriptive statistics.

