## 8.6 Efficacy analyses

Responder-type endpoints (ACR20, ACR50, ACR70) will be summarized with response rates and 95% confident intervals (CI) by treatment group and visit.

Observed and change from baseline in continuous endpoints (tender joint counts, swollen joint counts, PGA of disease activity, PtGA of disease activity, patient’s pain assessment, HAQ-DI, acute-phase hsCRP, ESR, SF-36) will be summarized by treatment group and visit with n, mean, SD, median, and range. No statistical tests will be performed.

At the start of the long-term extension study, each subject will continue to receive the same dose

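### At visits where the original schedule draws no hsCRP, the SAP's missing-component rule drops attending subjects whose ACR status turns on hsCRP, so by-visit ACR rates are not like-for-like

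*SAP*

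**What the plan says.** - **Endpoint.** SAP 4.1 lists "The proportion of subjects who achieve ACR20 at measured time points", with ACR50 and ACR70 in the same form. The ACR20 requirement reads: "20% improvement from Baseline in both tender joints (68) and swollen joints (66) along with at least a 20% improvements in 3 of 5". Those five are the physician global, patient global, pain, HAQ-DI and CRP.
- **Display.** SAP 8.6: "Responder-type endpoints (ACR20, ACR50, ACR70) will be summarized with response rates and 95% confident intervals (CI) by treatment group and visit". SAP 8.1 keeps unscheduled results out of the summary tables.
- **Incomplete components.** SAP 4.1 uses whichever components are present, and then: "else if the available non-missing components are not sufficient to determine the response status of ACR endpoint then it is considered missing". SAP 7.2.1 adds that, in general, "missing values for any of efficacy and safety endpoints will not be imputed when summarizing these endpoints using descriptive statistics".
- **Schedule.** SAP Table 1 (original protocol) marks the row "Tender and Swollen Joint counts", the three VAS rows and HAQ-DI at Weeks 0, 8, 20, 32, 44, 56, 68, 80, 92 and 104, and at some later visits. Up to Week 104, the shared hsCRP/ESR row is marked only at Weeks 0, 8, 32, 56 and 104.
- **Older laboratory values.** SAP 3.1 allows them in one place, the parent Week 52 response used for eligibility: "using Week 48 laboratory data from the parent study where relevant for calculations".

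**The concern.** Nothing in SAP 4.1 or 8.6 limits the ACR rates to visits at which hsCRP is drawn. At the other visits a subject can attend, complete every scheduled assessment and still have no ACR status, because the schedule never asked for the deciding item. ESR cannot stand in, since it shares the hsCRP row. The subjects removed are the borderline ones, so the loss depends on outcome.

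Entry requires ACR20 response at parent Week 52, so the extension series mainly describes whether response is maintained. A subject who slips from three qualifying items to two is the case of interest. That subject can be classified at a visit with hsCRP and is dropped at a visit without it. Part of any visit-to-visit movement could then come from the blood-draw calendar, and the confidence intervals would not show it.

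**Working it through.** The plan states no figure on this point, so there is none to reproduce.

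**1. Affected visits.** Setting the two sets of rows side by side, five of the nine post-baseline ACR visits through Week 104 have no hsCRP: Weeks 20, 44, 68, 80 and 92. Two of the four before Week 52 are affected: Weeks 20 and 44. Columns after Week 104 are visibly displaced in the extracted table, so nothing here rests on them. As a cross-check, the hsCRP/ESR weeks in amended Protocol 9.1.3.1.2 (8, 20, 56, 104, 152, 200) also omit 44, 68, 80 and 92. On that list the pre-Week-52 gaps would be 32 and 44, so two of four either way.

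**2. Who is dropped.** Without CRP, six components (two joint counts, four items) give 2^6 = 64 improved/not-improved patterns.

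- Certain response (both joint counts, at least 3 of 4 items): 4 + 1 = 5.
- Undetermined (both joint counts, exactly 2 of 4 items): 6.
- Certain non-response: 64 − 5 − 6 = 53.

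When the other components are complete, the rule therefore removes exactly the subjects whose status turns on hsCRP.

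**3. Effect on the rate.** Among attending subjects with the other components complete, let r = share certain to respond, u = share undetermined, and c = fraction of the undetermined whose hsCRP would have qualified.

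- Rate under the SAP rule: r/(1−u).
- Rate under the full definition: r + uc, which lies between r and r+u.
- Difference: r/(1−u) − r − uc = u × [r/(1−u) − c].

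The two agree only if c = r/(1−u). The gap is positive when c is smaller than that, negative when it is larger, and never exceeds u in size.

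**4. Numbers.** The documents give no r, u or c, so all values are assumptions.

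| r | u | SAP rule | Full definition, c from 0 to 1 | Difference (points), c from 1 to 0 |
|---|---|---|---|---|
| 0.80 | 0.05 | 0.842 | 0.800–0.850 | −0.8 to +4.2 |
| 0.75 | 0.07 | 0.806 | 0.750–0.820 | −1.4 to +5.6 |
| 0.60 | 0.08 | 0.652 | 0.600–0.680 | −2.8 to +5.2 |
| 0.30 | 0.10 | 0.333 | 0.300–0.400 | −6.7 to +3.3 |

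Take the second row with c = 0.5. The full definition gives 0.75 + 0.07 × 0.5 = 78.5%, against 80.6% under the rule. With no change in disease, Weeks 8, 20, 32, 44 and 56 would read 78.5, 80.6, 78.5, 80.6 and 78.5.

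**5. Plausible size.** A simulation with a common latent normal factor was run under assumed component improvement rates: joint counts 0.50–0.85, other items 0.35–0.80, CRP 0.35–0.60. The common factor carried 0.5 or 0.7 of the latent variance of the clinical components and 0.2 or 0.5 of that of CRP.

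| Scenario | u | Difference (points) |
|---|---|---|
| ACR20-like | 4.8–6.4% | +1.3 to +1.9 |
| ACR20-like, lower response | 6.9–9.1% | +0.5 to +0.8 |
| ACR50-like | 6.8–8.8% | −1.0 to −0.1 |
| ACR70-like | 6.8–7.8% | −2.8 to −1.3 |

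A second simulation, conditioned on ACR20 response at entry with all items improving equally on average, gave u of about 2–10% for ACR20. The differences were about −0.5 to +0.3 points for ACR20 and −2.4 to −0.4 for ACR50/70. Together: u about 2–10%, difference about −3 to +2 points.

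**The case against.** The strongest case on the other side is that this matters little. SAP 2.3 records that the amended protocol removed the efficacy objectives, and SAP 5 makes safety the leading primary objective. No tests are planned and no decision is tied to a by-visit ACR rate. SAP 3.1 ends efficacy assessment once all subjects have switched to open-label dosing. All of that stands, and it limits the weight of the point. It does not remove it: SAP 4.1 and 8.6 still specify the analysis, and SAP 8.9 plans an interim review of efficacy after the last subject's Week 52 visit. On the SAP's timing, Weeks 20 and 44 precede the switch. Weeks 68, 80 and 92 count only for subjects still assessed for efficacy then.

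The phrase about measured time points could also be read as meaning only visits with all components. The SAP does not say so; if that was the intention, one sentence would settle it.

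A reader might infer more than the documents support:

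- *That the rates are biased in a known direction.* The sign depends on c, which nothing in the documents fixes, and the simulated ACR20 range includes zero.
- *That very many subjects are lost at each visit.* Undetermined shares as high as 18% come from assuming an unselected population, which ignores the responder entry criterion. Multiplying by 286 treats an enrolment ceiling as attendance.
- *That visits with hsCRP use everyone.* The same missing-component and no-imputation rules apply there to missed assessments and dropouts. The difference is that those gaps are not built into the schedule.
- *That the plan already carries hsCRP forward.* The Week 48 value is 4 weeks old and serves eligibility only. Here the value would be 12 weeks old at Weeks 20, 44 and 68, 24 at Week 80 and 36 at Week 92.

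**Conclusion.** The point holds as a defect of definition. With the schedule as printed, the SAP's rule makes ACR status undeterminable at Weeks 20 and 44 for attending subjects who meet both joint criteria and exactly two of the four other items. It then removes them from numerator and denominator. The same applies at Weeks 68, 80 and 92 where efficacy was still assessed. Rates at these visits estimate something different from rates at visits with hsCRP, unless c happens to equal r/(1−u), and no passage supports that.

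Under assumed inputs the difference is about −3 to +2 points, with a sign that changes with the threshold. That can produce a visit-to-visit zigzag in a descriptive analysis of secondary importance; it would not change the safety conclusions. The size rests wholly on assumed r, u and c. The list of visits rests on Table 1 as extracted and should be confirmed against the original.

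**What to change.** Amend SAP 4.1 and 8.6 as follows.

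1. Report ACR20/50/70 point rates with 95% CIs only at visits with scheduled hsCRP. Confirm the weeks, including those after Week 104, against the original table.
2. At other ACR visits, keep undetermined subjects in the denominator. Show their number and the bounds r to r+u by treatment group.
3. If a point value is wanted there, use the most recent scheduled hsCRP as a labelled sensitivity derivation. State the age of that value and how many statuses rest on it.
4. Keep the individual components at every visit where they are measured.

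The cost is SAP wording and a small programming change; no new data are needed. The downside is fewer ACR point estimates, or an interval in place of a point at some visits.

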## 4.2 Safety endpoints

The safety endpoints of this study are:

- Adverse events (AEs)
- Laboratory assessments
- Suicidal ideation and behavior (C-SSRS)
- Vital signs
- ECG
- Physical examination
- ADA to tildrakizumab

## Statistical Analysis Plan (SAP)

### 5 SAMPLE SIZE AND POWER

The sample size of this study is determined by the number of subjects who rollover from the parent PsA study. No power is calculated because 1) the study is populated with subjects consenting to extended treatment, and 2) the leading primary objective is to assess the long-term safety of tildrakizumab.

# Statistical Analysis Plan (SAP)

## 6 ANALYSIS POPULATIONS

### 6.1 All Subjects as Treated (ASaT) Population

The All Subjects as Treated (ASaT) population consists of all subjects who entered the extension study and received at least 1 dose of IMP. The ASaT is the primary population for safety/tolerability, efficacy, and PK analyses. The analysis will be based on the treatment subjects actually received.

